### **Scheduling study procedures.**

#### Aim 1: Formative Research

**Formative User Study.** After teleorientation, eligible participants are scheduled to attend the formative user study; a total of 30 participants will be scheduled.

#### Aim 2: Pilot RCT

**Pilot RCT.** After teleorientation, RCT participants are scheduled for a baseline assessment visit. During the baseline visit, a trained study coordinator performs fMRI screening and data acquisition and collects baseline data per standardized measurement protocols. Females of child-bearing age who indicate any possibility that they may be pregnant must take a point-of-care urine pregnancy test. At the end of the baseline visit participants receive instructions to complete the initial ecological daily assessment for the next 7 days. Following successful completion of the baseline measures, fully eligible, consented participants are randomized to either Group A (Lumen Intervention) or Group B (waitlist control), at a 2:1 allocation.

## **6.0 Study Design and Procedures**

#### Aim 1: Formative Research

**Scenario-based evaluations** do not include human subjects. These evaluations are carried out by 2 independent PST master trainers as contracted members of the research team, each of whom will assume the role of patients and interact with Lumen to complete 8 scenarios of PST encounters. These scripted scenarios will be based on previously recorded encounters with live counselors to broadly exploit various aspects of PST. After each scenario, they will provide feedback on quality and appropriateness of their interactions with Lumen.

The **formative user study** includes 30 participants with low, medium, or high digital health literacy based on the Digital Health Literacy Instrument. After consent is obtained qualified study staff, each participant will complete a full PST session with Lumen in up to each of four 1-hour sessions. In addition, participants will download the paired application on their smartphones to test notifications, surveys, and ecological daily assessments. The formative research version of the Lumen PST session utilizes mock scores of recent psychological symptoms (PHQ-9 and GAD-7). Participants will only complete user-experience assessments and provide open-ended qualitative feedback on the interactive demo. Designated members of the study team (e.g. a researcher and a Lumen developer) will unobtrusively observe and listen to participant interactions with Lumen and take observation notes regarding critical incidents during the interaction (e.g., breakdowns in the conversation) and technical issues that were encountered. The modality of these unobtrusive observations (e.g. Zoom if conducted remotely, or from behind a one-way mirror if conducted in-person) will be determined by following the latest COVID-19 safety guidelines and precautions. Post-completion, participants perform a retrospective cognitive walkthrough to verbally describe their interaction with Lumen with the researcher. Cognitive walkthrough methods are commonly used for design and help in ascertaining the “cognitive fit” between the system and its users. Specific emphasis during the walkthrough will be on participant interaction with Lumen: what worked (and what did not), breakdowns in the interaction, understanding of developed solution implementation plan, perceptions regarding the viability of their plan, and general comments regarding the interaction. The researcher and developer may prompt participants with additional questions based on their observation

notes. Following cognitive walkthroughs participants complete 3 user surveys: (1) NASA Task Load Index (NASA-TLX) of user workload along with 6 dimensions of mental, physical, temporal, performance, effort and frustration, (2) User Experience Questionnaire-Short version (UEQ-S), and (3) the Working Alliance Inventory adapted for digital interventions (WAI-Tech). Survey data is collected via REDCap. Lastly, the 2 PST master trainers will evaluate audiorecorded Lumen PST sessions on: (1) treatment fidelity based on the 7-item PST Adherence and Competence Scale (PST-PAC), (2) completeness, consistency, and quality of the solution plan, and (3) perceptions of Lumen.

### Aim 2: Pilot RCT

The objective of the pilot RCT is to demonstrate (1) the feasibility of participant recruitment and retention, (2) participant acceptability of Lumen for PST, and (3) engagement of neural targets subserving emotional reactivity and cognitive control (i.e., target engagement).

**Randomization and blinding.** A designated staff person performs randomization using an online system that [name] and team published. The system is a modern implementation of Pocock and Simon's minimization, a covariate-adaptive method to achieve better-than-chance marginal balance between study arms across multiple key baseline characteristics. Minimization accommodates a greater number of balancing covariates than does stratified randomization. The system's computational algorithm automatically adjusts the randomization probability based on the characteristics of all the previously randomized participants, thus minimizing the total covariate imbalance between arms after each new participant is randomized. In this study, randomization covariates include sex, age, race/ethnicity, education, digital health literacy, PHQ9, and GAD7. Note that, aside from eligibility screening, PHQ9 and GAD7 are also process measures used to monitor treatment progress throughout PST sessions. Their inclusion among randomization covariates helps avoid accidental bias at baseline. The online system applies Efron's biased-coin method to protect allocation concealment with the use of nonextreme randomization probabilities, and the staff person(s) using the system has/have no deep knowledge of the backend coding or execution and no ability to manipulate it. By design, treatment assignments are identifiable to participants, but blinding of outcome assessment, event adjudication, and data analysis will be enforced. To accomplish the 2:1 allocation, participants are randomized into 3 sets, and then 2 of these sets will be combined to form the Lumen group. The remaining set forms the waitlist control group. This method both protects blinding and preserves the allocation ratio at every allocation as per Kuznetsova and Tymofyeyev. The same method is used in the ongoing ENGAGE-2 study.

**Assessments.** All participants complete two study assessment visits, at baseline (week 0) and at 16 weeks, and self-complete ecological daily assessments for 7 days every 2 weeks. The fMRI scan visits are conducted at the 3T MR Research Program located at the UIMC Advanced Imaging Center, a BioRAFT registered facility, and SPEAC study staff work in compliance with all COVID-19 safety guidelines employed by facility management. When scheduling assessment visits, study coordinators instruct participants in the current COVID-19 safety precautions prior to and at the visits.

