## 1.0 Project Summary/Abstract

Depression and anxiety are the leading causes of disability and lost productivity, and are often underdiagnosed and undertreated owing to access, cost, and stigma barriers. Novel and scalable psychotherapies are urgently needed. Advances in artificial intelligence (AI) offer a transformative opportunity to develop intelligent voice assistants as virtual health agents accessible on personal devices. Meanwhile, major advances in human neuroscience have fueled a paradigm shift to study brain mechanisms underlying behavioral health interventions. Leveraging emerging science in these transdisciplinary areas, this project aims to develop and rigorously test a novel voice-enabled, AI virtual agent named Lumen, trained on Problem Solving Therapy (PST), for patients with moderate, untreated depressive and/or anxiety symptoms. The project will investigate the effect of Lumen on engagement of a priori neural targets—amygdala for emotional reactivity and dorsal lateral prefrontal cortex (DLPFC) for cognitive control—as putative mechanisms. The project has 2 phases: R61 and R33 (see Figure 1). Phase 1 is the R61 phase (years 1-2) and will be the sole focus of this protocol. Focusing on Lumen development and refinement as well as pilot testing, Phase 1 has 2 specific aims. Aim 1 on Lumen development and refinement will proceed in 2 stages: (1) scenario-based clinician evaluations, and (2) a formative user study (n=30 participants). Aim 2 is to pilot test Lumen in a 2-arm randomized clinical trial (pilot RCT), among 60 participants with moderate, untreated depression and/or anxiety who are randomized in a 2:1 ratio to receive PST with Lumen (n=40) on a secure study iPad or be on a waitlist (n=20). At weeks 0 and 16 participants will complete functional magnetic resonance imaging (fMRI) to assess neural target engagement as well as validated surveys of patient-reported outcomes (PROs) (e.g., depressive and anxiety symptoms, functioning, quality of life). In addition, participants will complete ecological daily assessments of mood, stress, appraisal and coping for 7 days every 2 weeks during the 16-week follow-up period. The Phase 1 milestones are (1) establishing the functionality, usability, and treatment fidelity of Lumen; and (2) demonstrating feasibility, acceptability, and neural target engagement. Achieving these milestones will provide the basis for the future R33 phase (Phase 2) focused on examining target engagement and PROs in a larger 3-arm RCT by comparing Lumen with a waitlist control arm and an in-person PST arm. This protocol only focuses on the R61 phase.

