## Appendix 3. Power analysis and statistical analysis plan – Aim 2 Pilot RCT

### A. Power Analysis

The primary objective of the Pilot RCT in the R61 phase is to evaluate neural target engagement based on the criteria (specified in B.1 below) in order to transition to the R33 phase. Research to examine neural targets as mechanisms of psychotherapy is an emerging field. No prespecified treatment difference of clinical importance or established effect sizes are available for our proposed neural target measures from fMRI. To address such early stage research, Julious recommended that rather than powering in the traditional fashion to test a formal hypothesis of a (in truth unknown) desirable treatment difference, the sample size be selected in order to provide a given level of precision of the treatment effect estimates using the confidence interval (CI) approach, which Ma et al. have used in a completed NIH-funded pilot RCT. Specifically, Julious and others recommended the use of precision intervals of prespecified standardized width to guide sample size determination. Julious offered a further refinement to provide *Assurance* (akin to power) that a chosen standardized width of the precision interval contains the true mean treatment difference. To obtain a precision interval with a 2-sided standardized half-width of 0.5 (akin to a medium effect size) with 90% assurance, we have planned a sample size of 60 ( $n_{Trt}=40$ ,  $n_{Con}=20$ ), assuming  $\geq 85\%$  retention at 16 weeks. This will provide reliable estimates of *meaningful improvement* from week 0 to 16 in amygdala activity for nonconscious threat-related reactivity and in DLPFC activity for cognitive control among Lumen participants, compared with waitlist controls (target engagement criterion (1); see below). Tests of the 2 *a priori* neural targets—amygdala for emotional reactivity and DLPFC for cognitive control—are regarded as separate inferential domains, that is, not within one family of comparisons, and thus are not corrected for multiplicity (or familywise error rate) across domains. Importantly, as explained, the objective of the Pilot RCT is not to claim statistical significance of a prespecified key hypothesis but to obtain reliable effect estimates with precision for a decision on transition to the next phase. In this context, multiple testing is not required or recommended.

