The SPEAC project is at the frontier of research on developing a voice-based AI agent (Lumen) for PST and validating its effect on *a priori* neural targets, and the Pilot RCT (Study 1) is to estimate possible effects of target engagement, which, if promising, will support further investigation to confirm target engagement in Study 2. In this context, we apply a precision interval approach (see Section A above) to determine Criterion 1. We define that, compared with the waitlist control group, the Lumen PST treatment group will demonstrate a *meaningful improvement* in a neural target if the standardized between-group mean difference is at least Cohen's  $d=0.3$  in favor of Lumen (small effect; 50% of that in ENGAGE). At this effect size, the upper limit of the precision interval overlaps with  $d=0.8$  (large effect) given a standardized half-width of 0.5 with 90% assurance that the interval contains the true mean difference based on the power analysis. We consider such a finding to be meaningful and will suffice Criterion 1.

- ii. Criterion 2. Change in the level of task-evoked activation of a neural target that meets Criterion 1 correlates with temporally concurrent change from week 0 to 16 in self-reported measures within the corresponding PST theory-based construct for emotional reactivity or cognitive control. As noted, we consider correlations of  $r=0.4$  or greater meaningful. Specifically:
  - a. If the amygdala target exhibits a meaningful improvement in the Lumen group vs. the waitlist control (Criterion 1), then we will examine whether that improvement is significantly correlated with improvements in validated self-report measures of emotional reactivity (worry, affect) over the same 0-to-16-week interval.
  - b. If the DLPFC target exhibits a meaningful improvement in the Lumen group vs. the waitlist control (Criterion 1), then we will examine whether that improvement is significantly correlated with improvements in cognitive control (problem solving, dysfunctional attitudes) over the same 0-to-16-week interval.

Criterion 1 is tested via *t* test that compares the change from week 0 to 16 in the Lumen group with that change in the waitlist control group. Participants are analyzed based on the group to which they are assigned using all available data. The *t* test described above can be readily expanded for exploratory subgroup analyses by applying to each subgroup (e.g., female vs. male).

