### **B.2. Treatment effects on PROs and ecological measures**

Secondary analyses will compare differences in discrete changes in PROs from week 0 to 16 and trajectories of change based on intensive time-series ecological measures between the Lumen and waitlist control groups. Analyses of the treatment effects on PROs will employ the same *t* test approach as described above for testing Criterion 1 for target engagement.

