Longitudinal mixed modeling will be applied to analyses of the ecological measures (mood, stress, appraisal, and coping) where the design is  $\text{Group} \times \text{Time} = 2 \times 8$  as these measures will be obtained (using a validated measurement burst design) daily for 7 days every 2 weeks (on weeks 0, 2, 4, 6, 8, 10, 12, 16). During active treatment in the Lumen group, this will occur for 3 days prior to, the day of, and 3 days after each scheduled PST session. For waitlist controls, this will occur for 7 days starting on Sunday of each assigned week. This allows us rich and detailed information on ambulatory changes over the course of treatment, as well as estimates of proximal responses to treatment within 3 days immediately post a PST session. For example, using the means of ecological measures over the 3 pre-PST days (to avoid confounding estimates with proximal treatment response) in the Lumen group and the first 3 days in the waitlist control group every 2 weeks as DVs, we will characterize their trajectory of change in terms of orthogonal linear, quadratic, and cubic components. We also will examine regression spline versions of these trajectories for visualization and interpretation. In a more exploratory vein, for each set of 7 daily ecological measures, collected biweekly, we will use piecewise linear models to characterize proximal responses to treatment based on the change of the 3 post-treatment days' means from the 3 pre-treatment days' means (omitting treatment day 4) in the Lumen group and the corresponding biweekly change of the last 3 days' means from the first 3 days' means (omitting day 4) in the waitlist control group. As these differences are nested within the 8 biweekly measurement bursts, and thus can be examined longitudinally, we can consider whether there is change over weeks in patients' proximal responses to each PST session (in terms of the ecological measures). In all analyses, all available data for each DV will be used and missing data will be handled directly through maximum-likelihood estimation via mixed modeling, supplemented with imputation and sensitivity analysis (see Handling Missing Data in Section B.4 below).

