#### **B.4. Intention to Treat (ITT) and Handling Missing Data**

Clinical trials such as the one proposed must face the issues of dropout and missing data. We have put in place a strong plan to ensure maximum retention of participants through the course of the study, with a projected 85% or greater retention (see the *Recruitment and Retention Plan*). Data missing completely at random (MCAR) may be analyzed “as is” without imputation, as it does not introduce bias into estimates and inferences. More commonly, data are missing at random (MAR) owing to covariate-dependent events (e.g., irregular work shifts, children’s illness, transportation, and scheduling foul-ups). Our primary analysis technique, linear mixed models, is robust for MAR and provides unbiased estimates of model parameters without imputation. (One may impute as well, but the benefit is usually modestly improved power rather than changes to conclusions.) The more serious concern for behavioral interventions is the possibility that data will be missing not at random (MNAR). This occurs when dropout or missingness is related to the level of the outcome of interest (e.g., a participant’s level of depression or anxiety). If treatment is working well and symptoms of depression and anxiety have lessened, then participants may feel continuation in treatment is not necessary or beneficial. They drop out or miss sessions because the treatment seems to have worked. On the other hand, if participants experience no improvement in symptoms, they may drop out or miss sessions because they are discouraged that the treatment seems not to have worked. In either case, the loss of data is related to the outcomes under study and has the potential to bias the study’s conclusion about the intervention. Handling the problem of MNAR is difficult. First, there is no test for the presence of MNAR (*vs.* MAR). Second, there are many possible underlying sources of MNAR and there is no guarantee that explorations of missing data patterns will clearly reveal those sources. Third, missing data imputation for MNAR necessarily makes strong and untestable statistical assumptions, so that conclusions from imputed MNAR datasets must remain tentative. This picture reinforces our strong commitment to participant retention (see the Study 1 *Recruitment and Retention Plan*).

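### The PRO comparison leaves out the seven factors used to minimize allocation, and the plan does not say which form of t test applies under 2:1 allocation

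*Combined protocol and SAP*

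**What the plan says.** Section 6.0 (Randomization and blinding) describes Pocock-Simon minimization: "In this study, randomization covariates include sex, age, race/ethnicity, education, digital health literacy", followed by PHQ9 and GAD7. A biased coin is applied "with the use of nonextreme randomization probabilities"; its value is not given. Section 1.0 describes participants "who are randomized in a 2:1 ratio to receive PST with Lumen (n=40) on a secure study iPad or be on a waitlist (n=20").

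Appendix 3, B.1 assesses Criterion 1 by a t "test that compares the change from week 0 to 16 in the Lumen group with that change in the waitlist control group", with no covariates and no statement of whether the variance is pooled. B.2 carries this over to the PROs: "Analyses of the treatment effects on PROs will employ the same" t test. For the diaries, B.2 says "Longitudinal mixed modeling will be applied to analyses of the ecological measures (mood, stress, appraisal, and coping"), in a group-by-time layout with no covariates named.

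The Criterion 2 regressions adjust for baseline self-report and group only. Baseline characteristics enter a model only in the exploratory dosing analyses of B.3, which are confined to the Lumen arm.

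**The concern.** An analysis should normally reflect the factors that constrained the allocation. If arms are balanced on variables that predict the outcome, the difference between arms varies less from trial to trial than an unadjusted standard error assumes. PHQ9 and GAD7 measure the same symptoms as HADS, which Appendix 2 (footnote b) names as the outcome measure of depression and anxiety, so some prediction of change is plausible.

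The t-test form is a different matter and has nothing to do with minimization. Under 2:1 allocation a pooled test is sensitive to unequal SDs. If the waitlist arm varies more, the pooled standard error is too small; if the Lumen arm varies more, it is too large.

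At stake are the intervals and p values reported for symptoms, functioning and quality of life, in a pilot whose stated purpose (Appendix 3, A) is precise estimation.

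**Working it through.** **Inputs from the documents.** 60 randomized, 40 v 20; retention "with a projected 85% or greater retention"; seven minimization factors. Taking 85% in each arm gives 34 v 17 = 51 completers.

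**Assumptions, not in the documents.** The biased-coin probability (0.7 to 0.9), the share R² of the variance of change that the factors explain (0 to 0.5), the ratio of arm SDs (0.5 to 2), and the coding of the factors.

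**1. The plan's own figure.** Appendix 3, A sets its target as follows: "To obtain a precision interval with a 2-sided standardized half-width of 0.5 (akin to a medium effect size) with 90% assurance". In SD units,

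half-width = t × √(1/n₁ + 1/n₀), and √(1/34 + 1/17) = 0.297.

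For a two-sided 90% interval on 49 degrees of freedom, 1.677 × 0.297 = 0.498, and 51/0.85 = 60. The planned N is reproduced, using a common SD and no covariates. A 95% interval at 34 v 17 has half-width 0.597.

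**2. Leaving out the minimization factors.** Under perfect balance, the true variance of the difference is (1 − R²)σ²(1/n₁ + 1/n₀), while the unadjusted analysis estimates about σ²(1/n₁ + 1/n₀). The ratio of reported to true standard error therefore cannot go much above 1/√(1 − R²): 1/√0.8 = 1.12 at R² = 0.2, and 1/√0.7 = 1.20 at R² = 0.3. A non-extreme coin, seven factors and dropout achieve only part of this. Simulated three-set minimization merged to 2:1, with 60 randomized, 51 completers and no treatment effect, gave:

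| Coin | R² | Reported / true SE | Type I error, unadjusted | Mean SE, unadjusted to adjusted |
|---|---|---|---|---|
| 0.7 | 0 | 1.00 | 4.8% | 0.296 to 0.307 |
| 0.7 | 0.1 | 1.03 | 4.0% | 0.297 to 0.292 |
| 0.8 | 0.2 | about 1.05 | 3.7% | 0.296 to 0.273 |
| 0.8 | 0.3 | about 1.08 | 3.1% | 0.296 to 0.255 |
| 0.7 | 0.3 | 1.08 | 3.8% | 0.297 to 0.258 |
| 0.7 | 0.5 | 1.15 | 2.6% | 0.297 to 0.218 |

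Other runs gave ratios of 1.04 to 1.07 at R² = 0.2, and 1.12 at R² = 0.3 with coin 0.9. With coin 0.9 and R² = 0.1 there was no mismatch (1.00). Monte Carlo error at 3,000 runs is about 0.4 points on type I error and about 1/√(2 × 3,000) = 1.3% on the ratio. Adjusted analyses with ordinary standard errors had type I error of 4.2% to 5.8%. At R² = 0.2 and 0.3 (coin 0.8) the reported SE falls by 1 − 0.273/0.296 = 8% and 1 − 0.255/0.296 = 14%.

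**3. Unequal SDs at 34 v 17, if the test were pooled.** Pooled variance = (33 s₁² + 16 s₀²)/49, where 1 is Lumen and 0 is waitlist.

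- Waitlist SD 1.5, Lumen SD 1: pooled variance (33 + 36)/49 = 1.408; pooled SE √1.408 × 0.297 = 0.352; true SE √(1/34 + 2.25/17) = 0.402; ratio 0.88. Simulated type I error is about 8.6%.
- Lumen SD 1.5, waitlist SD 1: pooled variance (74.25 + 16)/49 = 1.842; pooled SE 0.403; true SE √(2.25/34 + 1/17) = 0.354; ratio 1.14. Simulated type I error is about 2.6%.

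Over wider ratios, pooled type I error is 6.9% to 11.3% when the waitlist SD is 1.25 to 2 times the Lumen SD, and 3.6% to 1.8% when the Lumen SD is 1.25 to 2 times the waitlist SD. Welch stays at 4.9% to 5.1% throughout.

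**4. Robust standard errors.** The adjusted model with HC3 standard errors gave type I error of roughly 2.5% to 3.6%, which brings back the conservatism that adjustment is meant to remove.

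**The case against.** The best defence has five parts.

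- **The mismatch is conditional.** It needs prognostic factors, and the documents give no R². Section 4.1 also restricts PHQ9 to 10-19 and/or GAD7 to 10-14, which may limit how much they predict. This stands, and it is why the result is given as a range.
- **The error is conservative and falls on secondary analyses of a pilot that disclaims significance testing.** This also stands. But a trial run for precision has more reason, not less, to use precision that its design already provides.
- **The plan never says the test is pooled.** Correct. A reader might infer an equal-variance test, but the text says only t test, so Welch is not ruled out. The gap is one of silence.
- **B.4 calls linear mixed models the primary technique and plans to impute covariates.** Those covariates are unnamed, and no between-arm model lists the minimization factors, so B.4 does not close the gap. Nor does it exclude the factors.
- **The diaries.** A reader might infer that the diary intervals are wrong too, since that model also names no covariates. This is not supported. The comparison there is group by time, and baseline main effects barely touch it. In one simulated dataset of 60 people and 8 occasions, adding seven baseline covariates left its standard error at 0.0828 with random intercepts and moved it only from 0.0913 to 0.0907 with random slopes.

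**Conclusion.** The point holds for the PROs, conditionally. The unadjusted standard error is about 5% too large at an assumed R² of 0.2 and 8% at 0.3, with type I error of about 3% to 4%. At R² = 0 there is no mismatch. The omission of the factors costs precision; it does not create false positives.

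The unstated t-test form is a separate gap. It matters only if the test is run pooled and the arm SDs differ, and only a larger waitlist SD makes it anti-conservative.

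It would be tempting to conclude that the go/no-go decision is compromised. It is not driven by this: B.1 defines meaningful improvement under Criterion 1 by a point estimate of at least d = 0.3, and no standard error enters that definition. For Criterion 1 only the reported interval and p value are affected.

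**What to change.** In Appendix 3, B.2, analyse PRO change from week 0 to 16 with a linear model of group plus the minimization factors: age, digital health literacy, PHQ9 and GAD7 as continuous terms, sex, and a few-level prespecified coding of race/ethnicity and education. Use ordinary model standard errors rather than HC3. Name the Welch form wherever a plain t test remains, including Criterion 1. Ordinary model errors still assume a common residual variance, so report the Welch comparison beside the adjusted one. Adjusting the diary models is optional and would need factor-by-time terms.

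The cost is SAP wording, since all the factors are already collected. Adjustment uses about 8 degrees of freedom, or more with finer coding. If the factors explain nothing, the standard error rises by about 3% to 5%. With 13 covariate columns it is 0.321 against 0.296 at R² = 0 (8% larger) and 0.302 against 0.296 at R² = 0.1, so the coding should be kept short. For the same reason the covariate change is aimed at the PROs and not at the neural targets, where the factors may predict little.
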